# 1 GENERAL INFORMATION

## 1.1 Introduction

Acne vulgaris is a chronic disease with devastating sequela of post-inflammatory hyperpigmentation (PIH) in patients with skin of color. The treatment of PIH in acne is complicated and controversial because some treatments such as topical retinoids may cause further PIH due to irritation.

There are several studies evaluating topical retinoids as well as Azelaic acid 15% gel. There is not much information about the effect of benzoyl peroxide and clindamycin combination in acne patients with skin of color except sub-analysis from a community based study with BP 5% and clindamycin combination at AM and a topical retinoid at PM regimen.

Therefore, the use of Onexton Gel as monotherapy in acne patients with only skin of color will be a novel contribution to our knowledge base.

## 1.2 Study Population

Twenty (20) subjects with skin of color who are 12 years of age or older with moderate facial acne vulgaris and moderate PIH on IGA scale

# 3 STUDY DESIGN

This is a single-center, open label pilot study. The study is comprised of 5 study visits; Screening, Baseline, and weeks 4, 8, and 16. All subjects will receive Onexton QD at Baseline. We will evaluate Investigator Global Assessment of acne (IGA), total lesion count, inflammatory lesion count, non-inflammatory lesion count, Investigator Global Assessment of PIH and distribution of PIH, adverse events and concomitant medications.

# 4 SELECTION AND WITHDRAWAL OF SUBJECTS

## 4.1 Inclusion Criteria

- i. Outpatient, subjects of skin of color, age 12 or older. Female subjects of childbearing potential must have a negative urine pregnancy test result at Baseline and practice a reliable method of contraception throughout the study;

*A female is considered of childbearing potential unless she is:*

- postmenopausal for at least 12 months prior to study drug administration;
- without a uterus and/or both ovaries; or
- has been surgically sterile for at least 6 months prior to study drug administration.

*Reliable methods of contraception are:*

- intrauterine device in use  $\geq$  90 days prior to study drug administration;
- barrier methods plus spermicide in use at least 14 days prior to study drug administration; or
- vasectomized partner.

*[Exception: Female subjects of childbearing potential who are not sexually active will not be required to practice a reliable method of contraception. These subjects may be enrolled at the Investigator's discretion if they are counseled to remain sexually inactive during the study and understand the possible risks in getting pregnant during the study.]*

- ii. Facial acne vulgaris in patients with skin of color ( Fitzpatrick Type V & VI Supplement VI) characterized by the following:
  - IGA Score for acne vulgaris 3
  - IGA Score for PIH 3
- iii. Able to understand and comply with the requirements of the study and sign Informed Consent/HIPAA Authorization forms.

## **4.2 Exclusion Criteria**

- i. Female subjects who are pregnant (positive urine pregnancy test), breast-feeding, or who are of childbearing potential and not practicing a reliable method of birth control.
- ii. Allergy/sensitivity to any component of the test treatment
- iii. IGA score for acne or 2 (mild) or 4 (severe)
- iv. IGA score for PIH or 2 (mild) or 4 (severe)
- v. Subjects who have not complied with the proper wash-out periods for prohibited medications (Supplement I).
- vi. Medical condition that, in the opinion of the Investigator, contraindicates the subject's participation in the clinical study.
- vii. Skin disease/disorder that might interfere with the diagnosis or evaluation of acne vulgaris
- viii. Evidence of recent alcohol or drug abuse.
- ix. History of poor cooperation, non-compliance with medical treatment, or unreliability.
- x. Exposure to an investigational drug study within 30 days of the Baseline Visit.

## **4.3 Withdrawal of Subjects**

It is the right and duty of the Investigator to discontinue the study participation of a subject when the subject's health or well-being is threatened by continuation in the study. Such subjects should be withdrawn from the study and not continued under a modified regimen.

The following are circumstances that would result in the subject's discontinuation from the study:

- the subject experiences a serious adverse event rendering them unable to continue study participation;
- the subject is unable to physically or mentally tolerate the use of the test medication;
- an exclusion criterion becomes apparent at any time during the study; or
- the subject voluntarily withdraws.

In the event of premature discontinuation from the study, the Investigator should determine the primary reason for discontinuation. A subject who is withdrawn from the study prior to initiation of treatment may be replaced.

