### **7.2.3 Follow-up and Final Reports**

Subjects who have had a serious adverse event must be followed clinically until all parameters, including laboratory values (if applicable), have either returned to normal or are otherwise explained. If death was the outcome of the event on the initial SAE Report, a Follow-up/Final Report, including autopsy report, when performed, must be completed.

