## **8 STATISTICS**

### **8.1 Sample Size Justification**

This is a pilot study and a formal justification for the sample size is not provided. The data from this study will provide important data for determining any trends regarding the safety and efficacy of study medication.

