### **8.2 Analyses**

Statistical analyses will be conducted on an intent-to-treat basis (i.e., all enrolled subjects will be included in the analyses). All statistical tests will be two-sided and interpreted at a 5% significance level. Descriptive statistics (i.e., mean, standard deviation, etc.) will be provided for all continuous variables and frequencies for all categorical variables collected in this study. These will be presented by treatment group. Summary tables will be used to present patient population characteristics at Baseline; data from the study questionnaires will be included. The incidence and severity of adverse and/or unexpected events will be tabulated and a complete listing of all reports of adverse and/or unexpected events will be presented.

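### Section 4.3 turns intolerance of the gel into exit from the study, so these subjects have no later PIH or lesion rating although every efficacy endpoint is at week 16

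*Combined protocol and SAP*

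**What the plan says.** Section 4.3 (Withdrawal of Subjects) describes one kind of exit. Its first paragraph deals with subjects whose health or well-being is threatened by staying in: "Such subjects should be withdrawn from the study and not continued under a modified regimen". A list then names the circumstances that end study participation. The one that matters here is that "the subject is unable to physically or mentally tolerate the use of the test medication". At exit, the investigator is asked only to establish the main reason.

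Section 3 and the schedule in 5.1.1 provide screening, baseline and weeks 4, 8 and 16. The end-of-treatment column is tied to week 16, and no early-termination visit is listed. Clinical follow-up after an event is required only where the event is serious: "Subjects who have had a serious adverse event must be followed clinically until all parameters" have resolved or been explained (7.2.3).

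Sections 6.1 and 6.2 place both co-primary endpoints (clear or almost clear on the acne IGA and on the PIH IGA) and all four secondary endpoints at week 16. Section 8.2 says: "Statistical analyses will be conducted on an intent-to-treat basis (i.e., all enrolled subjects will be included in the analyses". The plan gives no rule for a missing week-16 value.

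**The concern.** Section 4.3 merges two different events, stopping the gel and leaving the study. Anyone who cannot tolerate the gel stops being observed, while the outcome of interest is fixed at week 16.

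The timing matters for PIH in particular. Section 1.1 gives as a reason why treatment is difficult that "some treatments such as topical retinoids may cause further PIH due to irritation". PIH follows inflammation, so a pigment change set off by irritation could appear after the subject has gone. If so, those missing at week 16 are not a random subset of those enrolled. At stake are the week-16 PIH and lesion results in a study that section 8.1 says is meant to show trends in safety and efficacy. There is no control arm against which a distortion could be noticed.

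**Working it through.** **Inputs from the documents.** N = 20, one arm (1.2, 3). Ratings at baseline and weeks 4, 8 and 16 (3, 5.1.1). Entry requires PIH IGA 3 (4.1) on a scale of 0 to 6 (Supplement IV). The plan has no power, effect-size or dropout figure to reproduce: "This is a pilot study and a formal justification for the sample size is not provided" (8.1).

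**Assumptions.** The number of intolerance exits, w, is taken as 1 to 4, and the number of responders seen at week 16, r, as 8. The documents give neither.

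**Step 1: what is lost, by time of exit.**
- Before week 4: only pre-treatment ratings exist; three rating visits are lost (weeks 4, 8, 16).
- Between weeks 4 and 8: two visits are lost.
- After week 8: one visit is lost, and nothing is rated over the last 16 − 8 = 8 weeks.

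**Step 2: responder rate.** Exits counted as non-responders: r/20. Exits counted as responders: (r + w)/20. Rated subjects only: r/(20 − w). The gap between the first two is w/20, which is 5 points per exit whatever r is.

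| w | Exits as non-responders | Exits as responders | Gap | Rated only |
|---|---|---|---|---|
| 1 | 8/20 = 40.0% | 9/20 = 45.0% | 5 | 8/19 = 42.1% |
| 2 | 8/20 = 40.0% | 10/20 = 50.0% | 10 | 8/18 = 44.4% |
| 3 | 8/20 = 40.0% | 11/20 = 55.0% | 15 | 8/17 = 47.1% |
| 4 | 8/20 = 40.0% | 12/20 = 60.0% | 20 | 8/16 = 50.0% |

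For scale, the exact (Clopper-Pearson) 95% interval for 8/20 is 19.1% to 63.9%. Sampling error is already wide, and the gap comes on top of it.

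**Step 3: what a non-responder rule leaves open.** Suppose clear or almost clear means PIH grade 0 or 1 (Supplement IV uses other labels, so this mapping is an assumption). A subject entering at grade 3 is then a non-responder at any week-16 grade from 2 to 6. That covers improvement by one grade, no change, and worsening by up to three grades. The rule settles the co-primary count but says nothing about worsening. If x of the rated subjects worsen, the all-enrolled proportion lies anywhere from x/20 to (x + w)/20, again 5 points per exit. At one extreme, with w = 3, x = 0 and all three darkening after exit, the true figure is 3/20 = 15% (exact 95% interval 3.2% to 37.9%), while the rated subjects show 0/17 (0% to 19.5%).

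**Step 4: secondary endpoints.** Percent lesion reduction and change in PIH distribution have no natural non-responder value. If the unrated subjects' mean differs from the rated subjects' mean by D, the all-enrolled mean differs from the rated mean by (w/20) × D, that is 5% to 20% of D for 1 to 4 exits. The data collected give no estimate of D at week 16.

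**The case against.** The strongest reply is that the loss is limited and partly recoverable, and much of this stands.

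- Ratings made before exit remain. Under 7.1 a condition that worsens during the study is an adverse event, 7.2.2 has all such events recorded, and 8.2 tabulates and lists them. The reason for stopping is also established. An intolerance exit is therefore visible in the safety results.
- A reader might infer that the intent-to-treat analysis cannot be carried out. The documents do not support that. The co-primary endpoints are proportions, and a non-responder rule keeps all 20 in the denominator. Nor does 8.2 specify the rated-only rate in the table.
- A reader might infer that the most irritated subjects are never rated. The bullet covers any physical or mental intolerance, and a markedly irritated subject who tolerates the gel stays in and is rated.
- A reader might infer that the gel is known to cause PIH, or that the results are biased in its favour. Section 1.1 gives retinoids as its example and does not name the gel. An informative loss is plausible, not demonstrated.
- "This is a single-center, open label pilot study" (section 3), so no randomised comparison is damaged. Ratings taken off the gel may also reflect other treatment, so including them is a choice about what is being estimated.

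None of this supplies the observation that is missing. Pre-exit ratings and adverse events cannot show pigment change that appears after exit, and no imputation rule can either.

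**Conclusion.** The point holds as a limitation of data collection. Followed as written, section 4.3 and the schedule leave subjects who stop for intolerance without week-16 ratings, and 8.2 does not say what stands in for them. The size is 5 percentage points of best-to-worst-case range per lost subject: 5 to 20 points for 1 to 4 exits, a number that is assumed. For PIH worsening the same range remains even after a non-responder rule is adopted.

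That the loss is informative rests on section 1.1's general remark about irritation and on PIH following inflammation, not on anything stated about this gel. In a 20-subject single-arm pilot this is an inexpensive improvement worth making. It does not invalidate the study.

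**What to change.** The change concerns data collection and analysis only. All reasons for stopping the gel stay as they are, and so does the investigator's right to end a subject's participation.

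- **Section 4.3:** distinguish stopping study medication from leaving the study. Ask subjects who stop the gel and still consent to attend the remaining scheduled visits to week 16, or at least to be rated at exit and at week 16. The assessments are IGA acne, IGA PIH, PIH distribution, lesion counts, signs and symptoms, and adverse events.
- **Sections 3 and 5.1:** show these ratings in the schedule.
- **Section 8.2:** include the observed values in the all-enrolled analysis. List off-gel ratings separately, with any other treatment used.

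The cost is a short amendment to the protocol and consent form, and at most three already-scheduled visits for a few subjects (plus an exit rating if that option is chosen). The week-16 result will also contain some off-gel data, and the separate listing lets a reader see how much.

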## 5 TREATMENT OF SUBJECTS AND FOLLOW-UP

### 5.1 Study Procedures

#### 5.1.1 Assessment Schedule

	Screening 	Baseline		EOT
	Visit 1 0-28days	Visit 2 Wk 0	Visit 3, 4 Wk 4, 8	Visit 5 Wk 16
ICF/HIPAA ✓	X			
Subject Demographics/Medical Hx ✓	X			
Inclusion/Exclusion Criteria ✓	X	X		
Urine Pregnancy Test  ✓	X	X	X	X
Lesion Counts  ✓	X	X	X	X
Investigator Global Assessment Acne (IGA) ✓	X	X	X	X
Investigator Global Assessment PIH (IGA) ✓	X	X	X	X
PIH Distribution ✓	X	X	X	X
Subject assessments signs and symptoms stinging/burning and pruritus ✓	X	X	X	X
Signs and Symptoms (Investigator)  ✓	X	X	X	X
Study Medication Dispense ✓ Collect		D C	D C	C
Concomitant Medication/Treatment ✓	X	X	X	X
Adverse Events ✓		X	X	X

0 Screening and baseline can be the same day if subject does not need a washout

1 Female subjects of childbearing potential

2 Lesion Counts: papules, pustules, nodules, open/closed comedones

3 Peeling, erythema, dryness, oiliness

#### 5.1.2 Visit 1 & 2 (Screening/Baseline Visit)

- Informed Consent/HIPAA
- Urine Pregnancy Test (if applicable)
- Subject Demographics/Medical History
- Concomitant Medication/Treatment
- Investigator Assessments
  - IGA acne, IGA PIH, PIH distribution, Lesion Counts, Signs and Symptoms (peeling, erythema, dryness, oiliness)
- Inclusion/Exclusion Criteria
- Subject Assessments
  - Signs and Symptoms (burning, pruritus)
- Dispense study medication

#### 5.1.3 Visits 3, 4, (Week 4, & 8 ± 3 days)

- Urine Pregnancy Test (if applicable)
- Concomitant Medication/Treatment
- Adverse Events

- Subject Assessments
  - Signs and Symptoms
- Assess treatment compliance
- Investigator Assessments *IGA acne, IGA PIH, PIH distribution, Lesion Counts, Signs and Symptoms (peeling, erythema, dryness, oiliness)*

#### **5.1.6 Visit 5 (Week 16; ± 5 days)**

- Urine pregnancy test if applicable
- Concomitant Medication/Treatment
- Adverse Events
- Investigator Assessments *IGA acne, IGA PIH, PIH distribution, Lesion Counts, Signs and Symptoms (peeling, erythema, dryness, oiliness)*
- Subject Assessments
  - Signs and Symptoms
- Collect study medication

## **5.2 Study Treatment**

### **5.2.1 Details of Study Treatment**

Active ingredients of Onexton are clindamycin phosphate of 10mg in 1gm and benzoyl peroxide of 37.5mg in 1gm. Inactive ingredients include water, carbomer, homopolymer type C, propylene glycol, potassium hydroxide. It is dispensed 50gm in one bottle pump.

### **5.2.2 Dispensation and Dosage Schedule**

See supplement II

### **5.2.3 Treatment Assignment and Subject Numbering**

All subjects will receive the study medication. Study medication will be administered only to subjects included in this study following the procedures set out in the Study Protocol. All subjects who have signed an ICF will receive a 2-digit subject number, starting at 01. This subject number will be used to identify the subject throughout the study.

### **5.2.4 Supplies and Accountability**

The Investigator or pharmacist will inventory and acknowledge receipt of all shipments of study medication. All study medication must be kept in a locked area with access restricted to designated study personnel. The study medication must be stored in accordance with the instructions provided with the shipment. The Investigator or pharmacist will also keep accurate records of the quantities of study medication dispensed and returned by each subject. At study conclusion, all used and unused study medication will be destroyed as per the typical practice of the investigative site.

### **5.2.5 Treatment Compliance**

Subject compliance to the study treatment regimen will be verbally assessed at each visit; study personnel will ask each subject whether they missed any applications of study medication since the previous visit and will quantify the subject's response.

### **5.3 Concomitant Medication/Treatment**

Any necessary therapies that will not interfere with the response to treatment may be provided at the discretion of the Investigator. The use of any concurrent medication/treatment is to be recorded in the source.

## **6 ASSESSMENTS OF EFFICACY**

**6.1 Primary Efficacy Variable (Co-Primary endpoints will be the percent of subjects achieving clear or almost clear on IGA scale for acne and PIH at week 16.**

**6.2 Secondary Efficacy Variables: Secondary endpoints will be (1) the percent reduction of inflammatory lesion count at week 16. (2) percent reduction of non-inflammatory lesions at week 16. (3) percent reduction of total lesion count at week 16 (4) the change in PIH distribution at week 16.**

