### Supplement III

#### Investigator Global Assessment for Acne IGA)

The Investigator will evaluate the IGA using the following scale and **before assessing individual lesions counts:**

Score	Description
0 = Clear Skin	Clear Skin; no inflammatory or non-inflammatory lesions
1 = Almost Clear	Almost clear; rare non-inflammatory lesions with no more than one small inflammatory lesion
2 = Mild Severity	Mild severity; greater than Grade 1; some non-inflammatory lesions with no more than a few inflammatory lesions (papules/pustules only, no nodular lesions)
3 = Moderate Severity	Moderate severity; greater than Grade 2; some to many non-inflammatory lesions and may have some inflammatory lesions, but no more than one small nodular lesion
4 = Severe	Severe; greater than Grade 3; some to many non-inflammatory and inflammatory lesions, but no more than a few nodular lesions
5 = Very Severe	Very Severe; greater than Grade 4; many non-inflammatory and/or inflammatory lesions with some or many nodular lesions

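### Does percent reduction in lesion counts need a written formula, a zero-baseline rule and a median before this pilot can report it?

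*Combined protocol and SAP*

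**What the plan says.** The secondary endpoints in section 6.2 are "the percent reduction of inflammatory lesion count at week 16", the same measure for non-inflammatory and for total lesions, and the change in PIH distribution. None of the three lesion endpoints states a formula or a reference visit.

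Lesions are counted at every visit, including both Screening and Baseline. The schedule in section 5.1.1 allows up to 28 days between these two, with the footnote "Screening and baseline can be the same day if subject does not need a washout".

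Entry is by grade, not by count. Section 4.1 requires "IGA Score for acne vulgaris 3" and section 4.2 excludes "IGA score for acne or 2 (mild) or 4 (severe"). Supplement III describes grade 3 as "Moderate severity; greater than Grade 2; some to many non-inflammatory lesions and may have some inflammatory lesions".

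Section 8.2 is the whole analysis plan. It says "all enrolled subjects will be included in the analyses" and "Descriptive statistics (i.e., mean, standard deviation, etc.) will be provided for all continuous variables". Section 1.2 sets the size: "Twenty (20) subjects with skin of color who are 12 years of age or older". Section 8.1 says that this is a pilot without a formal sample size justification.

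**The concern.** A percent change needs a denominator, and the plan leaves it open in three ways.

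- Two pre-treatment counts can exist, and the plan does not say which is the reference.
- Grade 3 allows inflammatory lesions without requiring them, and there is no minimum count. An eligible subject could therefore start with none, which makes the percent undefined and sits awkwardly with analysing everyone enrolled.
- If the summary is a mean of per-subject percents, one subject with a very low starting count can pull it by several points at this sample size, and the median is not named.

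The pilot is meant to show trends. If these choices were made after seeing the data, the reported reduction could shift.

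**Working it through.** The plan gives no expected counts, standard deviation or effect size, so there is no figure of its own to reproduce. Every lesion count below is an assumption. Only n = 20 (section 1.2) and the entry grade (sections 4.1 and 4.2) come from the document.

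**1. Reference visit.** Take assumed counts of 30 at Screening, 24 at Baseline and 12 at week 16. The reduction is 100 × (30 − 12)/30 = 60% from Screening, or 100 × (24 − 12)/24 = 50% from Baseline. The choice matters on paper, but the document points to one answer. Sections 3 and 5.1.1 make Baseline the week 0 visit, when study medication starts. A Screening count can be up to 28 days older and would mix pre-treatment change into the result.

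**2. Pull of one subject.** With percent reduction = 100 × (Baseline − week 16)/Baseline, one more week-16 lesion changes that subject's value by 100/b and the mean by (100/b)/20 = 5/b points:

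| Baseline count b | Shift in mean (points) |
|---|---|
| 1 | 5.0 |
| 2 | 2.5 |
| 5 | 1.0 |
| 20 | 0.25 |

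In a constructed example, 19 subjects go from 20 to 10 lesions (50% each). If the last goes from 1 to 3 (−200%), the mean is (19 × 50 − 200)/20 = 37.5%. If the last goes from 5 to 6 (−20%), it is (950 − 20)/20 = 46.5%. The median is 50% in both, but only because 19 identical subjects fix it there.

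**3. How often a zero arises.** Counts were simulated as gamma-Poisson, with 20 subjects and 20,000 trials per setting. At assumed mean inflammatory counts of 20 to 25, some subject has a zero Baseline count in 0.7 to 6.5% of trials. In a deliberately low setting (mean 10, wide spread) the figure is 62 to 67%. Supplement III requires some non-inflammatory lesions at grade 3, so the non-inflammatory and total counts should not be zero at entry.

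**4. Mean against median.** If every subject has the same true 50% reduction, the mean of percents averages 39.3 to 46.9% at mean counts of 20 to 25, and the median about 50%. The median looks correct and the mean biased. That result depends on the common effect. Now let the remaining fraction vary between subjects (assumed CV 60%, average 0.5, no visit-to-visit noise):

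| Assumed mean count | Mean of percents | Median | Distance from 50 (mean; median) |
|---|---|---|---|
| 25 | 46.9 | 55.3 | 3.1; 5.3 |
| 40 | 48.2 | 55.4 | 1.8; 5.4 |

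Here the mean is closer to the average halving. With heavy visit-to-visit noise it is further away than the median. The ranking depends on assumptions that the documents cannot settle.

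**5. What section 8.2 already delivers.** It promises descriptive statistics for all continuous variables collected, which include the raw counts at each visit. Suppose 19 subjects go from 20 to 10 and the last from 0 to 2. The mean at Baseline is (19 × 20 + 0)/20 = 19.0 and at week 16 it is (19 × 10 + 2)/20 = 9.6. Mean absolute change is 19.0 − 9.6 = 9.4 lesions, using all 20 subjects. With complete data it follows from the reported means; only its standard deviation and interval would be new.

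**The case for a change.** The strongest reply is that a natural reading is not a written one. A sentence defining the formula costs almost nothing, and without it the reference visit, the handling of a zero and the choice of summary could be settled after the data are seen. The mean also falls below the median often: by 5 points or more in 28 to 73% of simulated trials at mean counts of 20 to 25 under a common effect. A related ambiguity points the same way. Section 6.2.1 heads papules and pustules as inflammatory and section 6.2.3 heads nodules as inflammatory too, without saying whether they are added together.

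Part of this stands. The definition is indeed unwritten, grade 3 does permit a zero inflammatory count, and the nodule headings leave a question. But a gap between mean and median does not show that either is wrong, since they measure different things, and the open-ended list in section 8.2 lets both be shown. A subject with a zero Baseline can only be left out of the percent summary and counted; that subject still appears in the raw-count summaries. Grade 3 allows at most one small nodule, so that question concerns at most one lesion per subject at entry. It is small unless the papule and pustule count is itself very low.

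**Conclusion.** No change to the plan is needed. The missing formula is a detail that an analyst would fill in the standard way: per-subject percent change from the Baseline visit, with any zero-Baseline subject reported by number. Preferring the median is a trade-off, not a correction, and adding absolute change gains little beyond the raw-count summaries already promised.

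The effect is confined to secondary, descriptive results in an open-label, single-arm pilot. No hypothesis, threshold or co-primary endpoint depends on it. A zero Baseline count is uncommon (0.7 to 6.5% of trials) if mean inflammatory counts are around 20 to 25. This is an assumption, and at much lower counts zeros would be frequent. Even then, the consequence is a few subjects missing from one percent summary, with their counts still reported. Writing the definition into section 6.2 would be tidy but is optional.
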